## STUDY DESIGN

### Summary

The study is a multicenter, three-arm, open-label, randomized, parallel-controlled trial, which plans to enroll 306 participants diagnosed with ATAAD from 7 hospitals in China. All patients receive TAR + FET procedure and are randomized to Group 1 (arch-clamping technique under mild hypothermia), Group 2 (arch-clamping technique under moderate hypothermia) and Group 3 (Sun's procedure using bilateral antegrade cerebral perfusion) in the ratio of 1:1:1. After a 1-year follow-up, the validity and safety of the mild hypothermic arch-clamping technique for ATAAD is

evaluated via the incidence of major adverse events including death, renal replacement therapy (RRT), stroke, and paraplegia, as well as times of circulatory arrest, cardiopulmonary bypass, and mechanical ventilation, and length of stay.

## **Rationale for Study Design**

- (1) Prospective: Prospective design minimizes bias. Standardized enrollment criteria, methods, process, and outcome measures, clarify the causal relationship.
- (2) Multicenter: Multicenter trials can enroll participants rapidly, resulting in shorter clinical trial periods, good extrapolation, and minimal bias caused by systematic errors.
- (3) Three-arm: This study involves two technical optimizations: temperature change from moderate temperature to mild temperature; unilateral antegrade cerebral perfusion changed to bACP. Due to the inability to control two variables simultaneously using a two-arm design, we plan to establish three groups for a randomized controlled trial.
- (4) Randomized: This trial uses randomization at each center. Each participant successfully screened has equal opportunity and is randomly assigned to Group 1 (arch-clamping technique under mild hypothermia), Group 2 (arch-clamping technique under moderate hypothermia) and Group 3 (Sun's procedure using bilateral antegrade cerebral perfusion) in a 1:1:1 ratio without the investigator nor the participant's personal preferences influence.
- (5) Open-label: The three surgical procedures differ significantly in terms of manipulation, so it is impossible to blind the researchers and participants.
- (6) Parallel-controlled: Sun's procedure as a TAR+FET technique, is the standard surgical treatment for ATAAD.

## **Subject Selection**

### **Inclusion Criteria**

- (1) Computed tomography angiography (CTA) confirmed as ATAAD according

to the 2022 ACC/AHA Guideline for the Diagnosis and Management of Aortic

Disease; Diagnosis consistent with ATAAD confirmed by aortic CTA;

- (2) Adult patients (18-70 years) weighing 50-120 kg;
- (3) Time interval between the onset of symptoms and operation is less than 14 days;
- (4) Indications for total aortic arch replacement are available;
- (5) Signed informed consent and availability for follow-up.

### **Exclusion Criteria**

- (1) History of chronic renal failure, hepatocirrhosis, and hepatic insufficiency;
- (2) Severe gastrointestinal complications of non-aortic dissection, such as mesenteric ischemia, gastrointestinal bleeding, hepatopancreaticobiliary dysfunction, and intestinal obstruction;
- (3) History of severe cerebral infarction (with cerebral infarction sequels);
- (4) Preoperative intubation or unconsciousness;
- (5) Inflammatory aortic diseases, such as Takayasu arteritis and Behçet's disease etc;
- (6) History of infectious aortic diseases;
- (7) History of cardiac and aortic surgery;
- (8) History of malignancy or previous radiotherapy;
- (9) Pregnant or feeding women, or anyone planning to reproduce during the test period;
- (10) Without informed consent signature;
- (11) Participating in any other clinical trial;
- (12) Having other causes not eligible for operation.

### **Criteria and Process for Participant Withdrawal**

All participants who sign the informed consent and qualify for the trial, regardless of time and reason for withdrawal, will be considered early withdrawals if

they have not completed the observation period.

(1) Withdrawal by investigators decision.

- Serious adverse events occurred, and the investigators determine that the trial should be terminated.
- Participants suffering from complications and special physiological changes that render them unsuitable to continue the trial.
- Poor compliance.

(2) Voluntary Withdrawal.

- Participant is unwilling or unable to continue participation for any reason and requests withdrawal.
- Participant does not explicitly request withdrawal but refuses further treatment and/or follow-up.

(3) Handling of Early Withdrawal

- All early withdrawals must be documented in the case report form, including completion of the study summary page and reason for withdrawal. After early withdrawal, the investigator should make every effort to contact the subject, inquire about the reason for withdrawal, and complete as many assessment items as possible.

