## Visit 2: Operation Day

- (1) All Subjects undergo TAR+FET procedure.
- (2) For subjects in the experimental groups undergo aortic repair using mild or moderate hypothermic aortic-clamping technique with bACP; for control group subjects, undergo aortic repair using Sun's procedure with bACP.
- (3) Record surgical details, including cross-clamping time, CPB time, circulatory arrest time, and type and volume of intraoperative blood transfusion.
  - Concomitant procedures: coronary artery bypass grafting, valve surgery, other procedures (branch arterial bypass, aortic sinus procedures).
  - Cross-clamping clamping time: Time interval between ceasing and restarting cardiopulmonary bypass when core temperature reaches moderate hypothermia.
  - CPB time: Start-to-end time of cardiopulmonary bypass to complete aortic repair.
  - Circulatory arrest time: from cessation to resumption of circulation.
  - Type and volume of intraoperative transfusion of red blood cells, platelets, plasma, cryoprecipitate.

## Visit 3: Postoperative Day 1

- (1) Collect symptoms and physical examination findings.

(2) Collect laboratory tests, including complete blood count, biomarkers of liver and renal function, etc.

(3) Collect the occurrence of death, RRT, stroke, and paraplegia.

(4) Collect ICU parameters:

- Duration of mechanical ventilation: Time interval between mechanical ventilation and extubation after operation.
- Length ICU of stay: Time interval from ICU admission to transfer or death.

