## **Analysis Populations**

Statistical analyses will be based on clearly defined analysis populations prior to data analysis in this study:

**Full Analysis Set (FAS):** The set constructed according to the intention-to-treat principle, including all subjects who participated in the study and received TAR+FET treatment.

**Per Protocol Set (PPS):** A subset of FAS, including all subjects who completed the trial without major protocol violations.

Baseline data will be analyzed based on the FAS, and analyses of primary and secondary outcomes will be performed on both FAS and PPS.

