## **Handling of Missing and Abnormal Values**

(1) Handling of missing data: No imputation of missing data will be conducted; analysis will be based on the data actually obtained.

(2) Handling of erroneous data: Investigators shall make written corrections to erroneous data. The database can only be locked after all errors have been corrected.

(3) Handling of unreasonable data: Investigators shall make written adjustments to unreasonable data. The database can only be locked after all unreasonable data entries have been addressed.

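### Investigators may withdraw patients after surgery because of events that are themselves the primary endpoint, and the PPS keeps only completers, so the endpoint can remove patients from the PPS

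*Combined protocol and SAP*

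**What the plan says.** Under Criteria and Process for Participant Withdrawal, investigators may withdraw a participant on three grounds. The first is "Serious adverse events occurred, and the investigators determine that the trial should be terminated". It mentions the trial, but the heading makes it a rule for individual participants. The second turns on the patient's condition and reads "Participants suffering from complications and special physiological changes that render them unsuitable to continue the trial". The third is "Poor compliance", which is not defined. Consented, eligible participants, "regardless of time and reason for withdrawal, will be considered early withdrawals if" their observation period is incomplete. Once someone has been withdrawn, contact is still to be sought, and the investigator is asked to "inquire about the reason for withdrawal, and complete as many assessment items as possible".

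The other relevant provisions are:

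- **Treatment.** Visit 2 has one intervention: "All Subjects undergo TAR+FET procedure". Everything after it is observation, to 12 months (Study Flowchart, Visits 3 to 7).
- **Endpoint and SAEs.** The primary composite is death, RRT, stroke and paraplegia. The Serious Adverse Events section covers death, life-threatening illness, permanent impairment and prolonged hospital stay.
- **FAS.** It leaves out only subjects who did not have TAR+FET or who have no follow-up records at all.
- **PPS.** It is a subset of the FAS, "including all subjects who completed the trial without major protocol violations". Its exclusion criteria also let investigators decide further exclusions case by case.
- **Analysis.** Primary Endpoint Analysis uses both FAS and PPS and does not say which decides. On missing data: "No imputation of missing data will be conducted".

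**The concern.** Withdrawal rules of this kind suit a treatment that continues and may have to be stopped. Here the treatment is over when the patient leaves the operating theatre, and the rules do not separate stopping treatment from stopping observation. A stroke, paraplegia or start of dialysis is both an event to be counted and a listed ground for withdrawal. The trial is open-label, so the decision is taken by people who know the arm, and no blinded review of withdrawals is described.

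The PPS definition turns this into an exclusion that depends on outcome. A patient withdrawn after a stroke has not completed 12 months. Read literally, neither has a patient who died. If such patients are dropped, event rates in the PPS are too low, and the difference between arms is distorted whenever dropping is not even. This matters most for the second test, Group 1 against Group 2. It is a non-inferiority test, for which the PPS result usually carries real weight.

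**Working it through.** **1. The plan's own figure.** For the first test: 13% vs 30%, one-sided 0.025, power 80%, 1:1 (Sample Size). With the pooled-variance formula and mean rate 0.215:

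n = [1.960·√(2·0.215·0.785) + 0.842·√(0.13·0.87 + 0.30·0.70)]² / 0.17² = 90.5, so 91 per group. Then 91/0.90 = 101.1, so 102 per group and 306 in total. The plan's figures reproduce.

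**2. What each set does with a patient withdrawn because of a primary event.**

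- *FAS:* the patient had TAR+FET and has records, so stays in. The recorded event counts, and a later event in the same patient does not change a composite incidence. The gap is a patient withdrawn for a non-endpoint reason who later has a first primary event. If it is not captured, it is lost, because nothing is imputed.
- *PPS:* the patient has not completed the observation period. No text treats death or another primary event as completion, so the patient can be dropped.

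**3. Size in the PPS, first test.** Let w be the share of patients with an event who are dropped. The documents give no value; 10%, 20% and 30% are assumptions. Start from 102 per arm and take dropped patients out of both numerator and denominator:

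- observed rate p′ = p(1−w)/(1−pw); analysed number n′ = 102(1−pw)
- probability of success = Φ[(d − 1.960·SE₀)/SE₁], where d is the control rate minus the Group 1 rate, SE₀ is the pooled and SE₁ the unpooled standard error

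With w = 0, SE₀ = 0.0575 and SE₁ = 0.0563, so power = Φ[(0.17 − 0.1128)/0.0563] = 84.5%.

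Dropping in both arms:

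| w | Group 1 | Control | Difference | Power |
|---|---|---|---|---|
| 0 | 13.0% | 30.0% | 17.0 points | 84.5% |
| 10% | 11.9% | 27.8% | 16.0 points | 81.3% |
| 20% | 10.7% | 25.5% | 14.9 points | 77.4% |
| 30% | 9.5% | 23.1% | 13.6 points | 72.6% |

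Dropping in the control arm only, w = 20%: 13.0% vs 25.5%, power 61%.

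Dropping in Group 1 only, with a true rate of 30% in both arms: at w = 20% the Group 1 rate appears as 0.24/0.94 = 25.5% on 95.9 patients. Then d = 0.0447, SE₀ = 0.0638, SE₁ = 0.0636, and the one-sided type I error is Φ[(0.0447 − 0.1250)/0.0636] = 0.10. At 10% and 30% it is about 0.05 and 0.19.

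**4. Size in the PPS, second test.** Put the true rates at the margin: 25% in Group 2 (the plan's assumption) and 30% in Group 1 (25% plus the 5% margin). With dropping in Group 1 only and the unpooled confidence interval, the chance of wrongly declaring non-inferiority is about 0.05, 0.11 and 0.20 for w = 10%, 20% and 30%, against 0.025.

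**5. Scale in patients.** At the planned rates 102 per arm gives about 13 events in Group 1 (102·0.13) and 31 in control (102·0.30). Twenty percent of these is about 3 and 6 patients.

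**The case against.** A reader might infer that primary events remove patients from the primary analysis altogether and bias both tests in both analysis sets. The documents do not support that. The FAS exclusions do not mention withdrawal, events are collected from day 1 onwards, and not imputing missing data deletes no recorded event. None of the figures above describes the FAS.

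The remaining FAS risk should also be modest. The definitions of RRT, stroke and paraplegia list observation points only up to discharge/30 days, and death after discharge is confirmed by telephone. Still, the flowchart and Visits 6 and 7 collect all four components at 6 and 12 months, so the risk is not nil.

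Other points on that side:

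- The SAE ground needs an investigator's determination and is not automatic. Consent and randomization come before surgery, so the grounds can also serve the preoperative period. Both are true, but nothing limits them to that period.
- Withdrawn subjects are still to be contacted and assessed. This softens the loss but is best effort. The firm commitment to complete the protocol visits is under Criteria and Procedures for Study Termination and covers the ending of the study, not of one patient's participation.
- The listed PPS exclusions do not name withdrawal. Dropping these patients follows from the completion requirement, so this is an ambiguity rather than a stated exclusion. It remains open, and the case-by-case clause widens it.
- The removal shares and one-arm patterns have no basis in the documents. They show sensitivity, not an expected result.

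**Conclusion.** The point holds for the PPS. As written, unblinded investigators can withdraw a patient because of an event that belongs to the primary endpoint, and that patient can then leave one of the two sets on which both primary tests are run. The ambiguity is most serious for the second test, since the plan does not say which set decides.

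If 10% to 30% of event patients were dropped evenly, power for the first test in the PPS would fall from 84.5% to between 81% and 73%. Uneven dropping is worse: in control only at 20%, power is 61%; in Group 1 only, type I error could reach about 0.05 to 0.19 for the first test. These results rest on the plan's rates, 102 per arm before dropping, and the assumed shares.

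For the FAS the conclusion is narrower: only a later first event, in a patient withdrawn for some other reason, can be missed. The sample size is not in error. This should be corrected, but it does not undermine the FAS analysis.

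**What to change.** - **Criteria and Process for Participant Withdrawal:** state that after surgery an SAE, a complication or poor compliance does not end outcome follow-up; that only withdrawal of consent does; and that scheduled visits to 12 months continue. This concerns data collection only and changes no clinical care.
- **Analysis Populations:** state that death or another primary event counts as completion for the PPS.
- **PPS Exclusion Criteria:** state that a primary event is not a ground for exclusion under the case-by-case clause.

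The FAS definition needs no change for this point. The cost is a wording amendment with ethics committee approval, and continued follow-up of a few patients at visits already in the schedule.

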## Criteria and Procedures for Study Termination

The clinical study should be suspended or terminated by the medical institution under the following circumstances, with full consideration of subject safety:

- (1) Violation of laws, regulations, or rules;
- (2) Breach of ethical principles or scientific integrity;
- (3) Discovery of serious quality defects in related drugs or medical devices during the study;
- (4) Identification of significant safety risks in the clinical study;
- (5) Existence of commercial bribery or other improper interests;
- (6) Misuse of research funds.

Investigators may apply to suspend or terminate the clinical study. Applications for suspension or termination must be reported to the clinical research management department with stated reasons. The medical institution will make decision in accordance with the full-process management system for clinical research. For enrolled subjects, the study treatment will be discontinued, and protocol-specified follow-up visits will be completed. Investigators will provide routine clinical care as needed according to each subject's actual situation.

## **EVALUATION METHODS**

### **Primary Outcome Measures**

Major adverse events include death, RRT, stroke, and paraplegia. The definitions, assessment methods, and observation time points for each indicator are as follows:

#### **(1) Mortality**

**Definition:** Death occurring within 30 days postoperatively or before final hospital discharge, including transfer to other acute care facilities.

**Assessment Method:** For in-hospital events, clinical death is declared when the patient's electrocardiogram shows asystole and declared clinical death. For post-discharge events, death confirmed by telephone follow-up.

**Observation Time Points:** Discharge day / postoperative 30 days and 12 months.

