Study Methods	
The study is a multicenter, three-arm, open-label, randomized, parallel-controlled trial, which plans to enroll 306 participants diagnosed with acute type A aortic dissection (ATAAD) from 7 hospitals in China. All patients receive total arch replacement (TAR) combined with frozen elephant trunk (FET) implantation and are randomized to Group 1 (arch-clamping technique under mild hypothermia), Group 2 (arch-clamping technique under moderate hypothermia) and Group 3 (Sun's procedure using bilateral antegrade cerebral perfusion) in the ratio of 1:1:1. After a 1-year follow-up, the validity and safety of the mild hypothermic arch-clamping technique for ATAAD is evaluated via the incidence of major adverse events including death, renal replacement therapy, stroke, and paraplegia, as well as times of circulatory arrest, cardiopulmonary bypass, and mechanical ventilation, and length of stay.

Outcome Measures	
1. Primary Outcome Measures
 
(1) Major adverse events include death, renal replacement therapy, stroke, and paraplegia
 
2. Secondary Outcome Measures
 
(1) Circulatory arrest time
 
(2) Cardiopulmonary bypass time
 
(3) Mechanical ventilation time
 
(4) Length of ICU stay

-------------------------	---

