**Table 1. The early-outcomes between arch-clamping technique and conventional TAR + FET procedure**

[figure not shown]
Variables	Arch-clamping	Conventional TAR	P value
	Technique (n = 39)	+ FET Procedure (n = 40)	
Circulatory arrest time, (min)	4.1 ± 0.6	23 ± 8.8	0.001
Cross Clamp time, (min)	96.9 ± 4.4	127.1 ± 13.3	0.001
CPB time, (min)	158.4 ± 6.8	198.0 ± 12.6	0.001
Postoperative drainage, (ml) *	465 ± 95.5	440.0 ± 100.5	0.260
Intubation time, (h)	13.6 ± 2.2	34.1 ± 14.3	0.001
Red blood cells transfusion, (U)	4.5 ± 1.5	4.1 ± 1.3	0.210
CRRT, n (%)	1 (2.6)	8 (20)	0.029
Stroke, n (%)	1 (2.6)	2 (5)	0.571
Thirty-day death, n (%)	2 (5)	3 (7.5)	1.000

Values are presented as n (%) or mean ± standard deviation. \* Postoperative 12-hour Drainage; *CPB*, Cardiopulmonary bypass; *CRRT*, Continuous renal replacement therapy.

Our team also try to elevate the core temperature of the circulatory arrest over 28°C. We compared the early outcomes of arch-clamping technique under different temperatures. The results demonstrated that the CPB duration and cross-clamp time were significantly reduced in the mild hypothermia group compared to moderate hypothermia group. Meanwhile, the mild hypothermia group has lower mortality and morbidities, especially for the incidences of stroke, spinal cord injury, and continuous renal replacement therapy (Figure 2) [11]. Our previous studies also found that using bACP as a brain protective strategy can significantly reduce the incidence of permanent neurological dysfunction [12,13]. Therefore, we hypothesize that arch-clamping technique combined mild hypothermia and bACP as a surgical bundle can be effective in minimizing the circulatory arrest time and mitigating multi-organ injury due to temperature changes and prolonged CPB duration.

In summary, we designed a multicenter randomized controlled trial to observe the 30-day and 1-year outcomes of patients with ATAAD after operation, seeking to validate the efficacy and safety of arch-clamping technique under mild hyperthermia

using bACP for the treatment of ATAAD.

**Figure 2.** Postoperative outcomes of using the arch-clamp technique in treating with ATAAD at different temperatures. Cardiopulmonary bypass time and cross-clamp time were presented as minutes; Total hospital stay was presented as days; Other variables were presented as n (%). *CRRT*, Continuous renal replacement therapy.

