**Table 3 Definition and Grading Criteria of Acute Kidney Injury**

Acute Kidney Injury	
Definition	Meets any one of the following: a. Increase in serum creatinine $\geq 0.3\text{mg/dL}$ ( $26.5\mu\text{mol/L}$ ) within 48 hours; b. Increase in serum creatinine to $\geq 1.5$ times baseline, known or presumed to have occurred within the prior 7 days; c. Urine output $<0.5\text{ mL/kg/h}$ for 6 hours.
Grading Criteria	Stage 1: Serum creatinine rises by an absolute value of $\geq 0.3\text{ mg/dL}$ ( $26.5\mu\text{mol/L}$ ), or increases by $\geq 0.5$ times but less than 1 time relative to baseline; or urine output $<0.5\text{ mL/kg/h}$ for $\geq 6$ hours but $<12$ hours.
	Stage 2: Serum creatinine increases by $\geq 1$ time but less than 2 times relative to baseline; or urine output $<0.5\text{ mL/kg/h}$ for $\geq 12$ hours but $<24$ hours.
	Stage 3: Any of the following: a. Serum creatinine $\geq 4.0\text{ mg/dL}$ ( $353.6\mu\text{mol/L}$ ); b. Serum creatinine increases by $\geq 2$ times relative to baseline; c. Urine output $<0.3\text{ mL/kg/h}$ for $\geq 24$ hours; d. Anuria for $\geq 12$ hours; e. Initiation of renal replacement therapy.

\* Due to intraoperative management interventions (such as mannitol administration), hourly urine output on the day of ICU admission will not be included in the assessment criteria for acute kidney injury.

**Observation Time Points:** Postoperative 1 to 3 days, and discharge day / postoperative 30 days.

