### **Study Procedures**

#### **Study Flowchart**

Point Items	Point 1	Point 2	Point 3	Point 4	Point 5	Point 6	Point 7
	Enrollment	Treatment			Follow-up		
	Emergency Admission	Operati on Day	Post-op Day 1	Post-op Day 2-3	Discharg e/30 ±7 Days	6 months ±7 days	12 months ±7 days
Informed Consent	X						
Medical History & Demographics	X						
Symptoms & Physical Examination	X		X	X	X		
Laboratorial Biomarkers							
Hemogram	X		X	X	X	X	X
Coagulation	X		X	X	X	X	X
Myocardial Injury	X		X	X	X	X	X
BNP	X		X	X	X	X	X
Liver Function	X		X	X	X	X	X
Renal Function	X		X	X	X	X	X
Electrocardiogram	X				X	X	X
Imaging Index	X				X	X	X
Primary Outcome *							
MAEs			X	X	X	X	X
Secondary Outcomes					X		
Circulatory Arrest Time		X					
CPB Time		X					
Duration of MV			X	X	X		
Length of ICU Stay			X	X	X		

\* Primary Outcome which include death, renal replacement therapy, stroke, and paraplegia;  
 MAEs, Major adverse events; RRT: Renal replacement therapy; CPB, Cardiopulmonary Bypass; MV: Mechanical Ventilation.

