### Visit 6: Postoperative 6 Months ( $\pm 7$ days)

- (1) Collect symptoms and physical examination findings.
- (2) Collect laboratory tests, including complete blood count, biomarkers of liver and renal function, etc.
- (3) Collect imaging data, including CTA and echocardiography.
- (4) Collect the occurrence of death, RRT, stroke, and paraplegia.

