## Statistical Considerations

### Sample Size

#### Estimation of Total Sample Size

Sample size estimation is performed using PASS 2021 software.

This study adopts a superiority design and a fixed sequence testing strategy. The primary outcome is the incidence of composite events, which is a low-benefit endpoint. The hypotheses are as follows:

- ① Experimental Group 1 is superior to the control group.
- ② Experimental Group 1 is non-inferior to Experimental Group.

The order of hypothesis testing is ①→②. According to the *Guideline on Multiplicity in Clinical Drug Trials*, this strategy will not inflate the overall Type I error rate (FWER), and no adjustment for multiplicity is required.

Based on previous research, the incidence of composite events with mild hypothermic aortic arch clamping combined with bilateral cerebral perfusion is approximately 13.64%, with moderate hypothermic arch clamping combined with unilateral cerebral perfusion is approximately 22.67%, and with the traditional Sun's procedure is approximately 29.63%.

For hypothesis ①, assuming the composite event rate is 13% in Experimental Group 1 and 30% in the control group, with a superiority margin set at 0, a one-sided significance level of 0.025, a power of 80%, and an allocation ratio of 1:1, at least 91 subjects are required in each group.

For hypothesis ②, assuming the composite event rate is 25% in Experimental Group 2 with a non-inferiority margin of 5%, at a one-sided significance level of 0.025, a power of 80%, and an allocation ratio of 1:1, at least 84 subjects are required

in each group.

In summary, taking the maximum required sample size above and allocating subjects in a 1:1:1 ratio among the three groups, and accounting for a 10% dropout rate, a total of 306 subjects will be enrolled in this study, with 102 subjects in each group.

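### The primary composite has no single time window: the text supports discharge/30 days, 12 months, or a mix, so the event rates that decide both tests are not fixed

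*Combined protocol and SAP*

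**What the plan says.** **Component definitions (Evaluation Methods, Primary Outcome Measures).** Death is "Death occurring within 30 days postoperatively or before final hospital discharge, including transfer to other acute care facilities", but its observation points are "Discharge day / postoperative 30 days and 12 months". RRT, stroke and paraplegia have no window in their definitions; each has the observation points "Postoperative 1 to 3 days, and discharge day / postoperative 30 days".

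**Design statements.** The Protocol Summary reads "After a 1-year follow-up, the validity and safety of the mild hypothermic arch-clamping technique for ATAAD is evaluated via the incidence of major adverse events", and the Study Design summary repeats it. The Background closes with the aim "to observe the 30-day and 1-year outcomes of patients with ATAAD after operation" and does not say which is primary.

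**Schedule.** The Study Flowchart has a primary-outcome row for major adverse events, footnoted as "Primary Outcome which include death, renal replacement therapy, stroke, and paraplegia". It is marked at day 1, days 2-3, discharge/day 30, 6 months and 12 months. Visits 6 and 7 each carry the instruction "Collect the occurrence of death, RRT, stroke, and paraplegia".

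**Planning and analysis.** Estimation of Total Sample Size says "the incidence of composite events with mild hypothermic aortic arch clamping combined with bilateral cerebral perfusion is approximately 13.64" percent, and gives 22.67% and 29.63% for the other two techniques, with no time window. Primary Endpoint Analysis defines T1, T2 and C only as incidences of composite events.

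**The concern.** T1, T2 and C are proportions of patients with an event by some time, and the plan does not say by when. Both decisions, superiority over the control group and non-inferiority to Experimental Group 2, are confidence limits on differences between these proportions. Testing is sequential, so the first verdict also decides whether the second test takes place.

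The trial is open-label. If the window is not fixed in advance, it could be chosen after outcomes are known, and nothing in the plan would contradict the choice. The planning rates cannot be matched to the endpoint either, because neither has a stated window.

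The denominator is also affected. Missing data are not imputed, so losses between day 30 and month 12 would change the rates under a 12-month reading but not under a 30-day one.

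**Working it through.** **1. The sections side by side**

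| Place | Death | RRT, stroke, paraplegia |
|---|---|---|
| Component definition | 30 days or final discharge | no window |
| Component observation points | discharge/day 30 and 12 months | days 1-3, discharge/day 30 |
| Protocol Summary, Study Design summary | after 1 year | after 1 year |
| Background aim | 30 days and 1 year | 30 days and 1 year |
| Study Flowchart, primary-outcome row | to 12 months | to 12 months |
| Visits 6 and 7 | collected at 6 and 12 months | collected at 6 and 12 months |
| Sample-size rates | none stated | none stated |
| T1, T2, C in the primary analysis | none stated | none stated |

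Three readings fit: (a) all components to discharge/day 30; (b) death to 12 months, the rest to discharge/day 30; (c) all components to 12 months.

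Reading (a) is itself incomplete. For the three non-fatal components the text does not say whether an event after discharge but before day 30 counts. The flowchart allows the visit at 30 ± 7 days, that is, days 23 to 37.

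**2. The plan's own sample size**

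Inputs from Estimation of Total Sample Size: 13% vs 30% (test 1); 13% vs 25% with margin 5 points (test 2); one-sided 0.025; 80% power; 10% dropout.

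Test 1, pooled variance, mean rate (0.13 + 0.30)/2 = 0.215:

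n = [1.960·√(2·0.215·0.785) + 0.842·√(0.13·0.87 + 0.30·0.70)]² / 0.17² = 90.5, rounded up to 91.

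Test 2, same form, mean rate 0.19 and distance 0.05 + 0.12 = 0.17: n = 83.005, rounded up to 84.

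Dropout: 91/0.90 = 101.1, rounded up to 102; 3 × 102 = 306. All stated figures reproduce.

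**3. How few events can separate two verdicts**

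Upper 95% limit = d + 1.96·√[p₁(1−p₁)/91 + p₂(1−p₂)/91], with d = p₁ − p₂. The plan names no interval method; Wald is shown with Newcombe as a check.

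| Test | Events of 91 | d | SE | Wald upper | Newcombe upper | Verdict |
|---|---|---|---|---|---|---|
| 1 (limit < 0) | 12 vs 22 | −0.1099 | 0.0572 | +0.0022 | +0.0041 | fails |
| 1 | 12 vs 23 | −0.1209 | 0.0577 | −0.0077 | −0.0058 | succeeds |
| 2 (limit < 0.05) | 12 vs 17 | −0.0549 | 0.0541 | 0.0511 | 0.0528 | fails |
| 2 | 12 vs 18 | −0.0659 | 0.0548 | 0.0414 | 0.0432 | succeeds |

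These counts were chosen at the boundary. They are illustrations, not forecasts.

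**4. Power if the planning rates are early rates and the endpoint is read at 12 months**

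The documents give no late-event rates, so every row after the first is an assumption. n = 91 per arm, one-sided 0.025.

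- Test 1: power = Φ{[|p₁−p₂|·√n − 1.96·√(2p̄(1−p̄))] / √(p₁(1−p₁) + p₂(1−p₂))}, with p̄ the mean of the two rates.
- Test 2: power = Φ{(0.05 − (p₁−p₂)) / √[(p₁(1−p₁) + p₂(1−p₂))/n] − 1.96}.

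| Rates: Group 1 / Group 2 / control | Test 1 | Test 2 |
|---|---|---|
| 13 / 25 / 30% (as planned) | 80% | 84% |
| +5 points in every arm: 18 / 30 / 35% | 74% | 77% |
| +10 points in every arm: 23 / 35 / 40% | 70% | 72% |
| ×1.1: 14.3 / 27.5 / 33% | 85% | 86% |
| ×1.2: 15.6 / 30 / 36% | 89% | 89% |

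For 80% power, the +5 row needs 105 (test 1) and 98 (test 2) per arm before dropout; the ×1.2 row needs 72 for each.

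**The case against.** The best counter-argument is that the component section is the operative definition and fixes discharge/day 30. Its introduction announces definitions and observation points for each indicator. The death definition excludes a death at month 8 unless it precedes final discharge, and the other three components stop at the same visit. The one-year sentence in the summaries also covers circulatory arrest and bypass times, which are fixed on operation day, so it may describe when evaluation happens rather than which events count. Visits 6 and 7 also collect laboratory and imaging data that are not endpoints. Table 1 reports thirty-day death, which hints that the planning rates are early ones.

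Much of this stands: the text leans towards discharge/day 30, and the three readings are not equally supported. It does not settle the matter. The Mortality entry adds 12 months against its own definition, the flowchart places 6 and 12 months under the primary outcome, and no secondary outcome gives the 12-month events another role. The planning rates are attributed only to previous research, so Table 1 is a clue and not a statement.

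The boundary counts also deserve the objection that any binary test has a count at which one event flips the verdict. Near the planned rates, 12 vs 27 of 91 gives an upper limit of −4.8 points; with Group 1 unchanged, the control arm would need five fewer events to fail. The counts show what is possible, not what is likely.

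**Conclusion.** The concern holds, and the plan is wrong as written on this point. Its sections contradict one another on the window of the only primary endpoint, and the two places that should decide, the sample-size section and the primary analysis, are silent. Different sections applied to the same data can give different primary event rates.

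The size of the effect cannot be determined from the documents. One event counted under one window and not another is enough to reverse either verdict if the result lies near its boundary. In the scenarios shown, test 1 power runs from 70% to 89% against 80% planned. Those figures assume that the planning rates are early rates, and they depend on how late events fall across arms. If the planning rates already match the window chosen, the 306 total stands.

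This must be fixed before any outcome comparison, because the window defines what the trial tests.

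**What to change.** - **Name one window for all four components** in Primary Outcome Measures and Primary Endpoint Analysis. For example: first occurrence of death, RRT, stroke or paraplegia from surgery through day X, in every patient, discharged or not. Day 30 is the time point common to all four components and would be a natural choice; 12 months is possible if the sponsor prefers it.
- **Count by event date**, not visit date, because the day-30 visit may fall anywhere from day 23 to day 37.
- **Say whether in-hospital events after day 30 count.** The present death definition includes such deaths; the other components are silent.
- **Label the other time point secondary**: the 12-month composite if day 30 is chosen, or the reverse.
- **State the window of the planning rates** in Estimation of Total Sample Size, and recheck power if it differs from the window chosen.
- **Align the remaining text**: the Protocol Summary, Background aim, Study Design summary, Study Flowchart, and Visits 5, 6 and 7.

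The cost is wording plus, if day 30 is chosen, a day-30 contact for patients discharged earlier; telephone follow-up is already foreseen for deaths after discharge. No extra patients are needed if the planning rates match the window; otherwise the power recheck decides.
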